8.3 Hypothesis and Methods of Analysis

Unless otherwise specified, continuous variables will be summarized by descriptive statistics including sample size, mean, standard deviation, median, minimum, and maximum.

Categorical variables will be summarized by frequency and percentage. Statistical analyses will use 2-sided 95% CIs unless otherwise specified.

[figure not shown]
8.3.1 Primary Effectiveness Analyses

[figure not shown]
The primary effectiveness analysis will estimate the proportion of patients, with corresponding 2-sided 95% CI, that achieve at least a 20% reduction from baseline Hour 0 IOP while on the same number or fewer IOP-lowering medications at Month 12 compared with baseline using a repeated measures logistic regression model. The model will include visit and baseline IOP as fixed effects with data from Months 1, 3, 6, 8, 10, and 12. An unstructured covariance matrix will be used for repeated measures on the same patient; if the model with unstructured covariance fails to converge, an alternative covariance structure will be chosen. The primary effectiveness analysis will be performed using the implanted population.

8.3.2 Secondary Effectiveness Analyses

The mean and 2-sided 95% CI for raw IOP with the corresponding change from baseline will be estimated using mixed effect model repeat measurement including all post-baseline visits with visit and baseline IOP as fixed effects with data from Months 1, 3, 6, 8, 10, and 12. An unstructured covariance matrix will be used for repeated measures on the same patient; if the model with unstructured covariance fails to converge, an alternative covariance structure will be chosen. Additionally, the number of IOP-lowering medications will be summarized by visit with descriptive statistics (mean, standard deviation, minimum, maximum) and 2-sided 95% CI for the mean. The secondary effectiveness analyses will be performed using the implanted population.

8.3.3 Other Effectiveness Analyses

8.3.4 Safety Analyses

Safety analyses will be performed using the implanted population. The number and percentage of patients reporting AEs will be tabulated regardless of causality. AEs, adverse device effects (ADEs), BCVA, line change in BCVA from baseline, biomicroscopic slit lamp, and ophthalmoscopy findings will be summarized by frequencies at each visit.

8.4 Subgroup Analyses

No subgroup analyses are planned.

8.5 Sample Size Calculation

Fifty patients will provide a precision of at least ± 0.145 to estimate the proportion of patients achieving an IOP reduction $\geq 20\%$ at 12 months on the same number or fewer IOP-lowering medications compared with baseline based on a 95% exact Clopper-Pearson CI. Sixty-five patients will be implanted to ensure at least 50 evaluable patients with 12 months of follow-up.

8.6 Interim Analyses

No interim analyses or reports are planned.

9. Materials

9.1 Study Treatment

9.1.1 Product Description

The XEN45 Glaucoma Treatment System is comprised of the XEN Gel Implant (also referred to as the Gel Implant) and the XEN Injector (also referred to as the Injector). The XEN Glaucoma Gel Implant is intended to create a channel through the sclera allowing flow of aqueous humor from the anterior chamber into the subconjunctival space to reduce IOP. The XEN Gel Implant is inserted using the XEN Injector via an *ab interno* approach, through a small corneal incision.

The XEN Glaucoma Treatment System is a sterile, single-use component. The XEN Injector is for single use only and is not reusable. Reuse may result in contamination, loss of function, and other undesirable side effects. The package must be examined to verify the appropriate model has been selected and product has not expired prior to implantation.

The inside diameter of the tube is approximately 45 μm , its outside diameter is approximately 150 μm , and it has a length of approximately 6 mm.

The XEN Gel Implant is composed of a gelatin derived from porcine dermis, formed into a tube, and then cross-linked with glutaraldehyde. The gelatin is designed to expand and become flexible when hydrated. The expansion of the tube's outer diameter also aids in retention of the Gel Implant in its intended location after surgical implantation.

The XEN Injector is a single use mechanical delivery system for the XEN Gel Implant. The Gel Implant is preloaded in the XEN Injector which houses the Gel Implant during insertion and delivery into the eye. The XEN Injector allows the surgeon to advance and deliver the Gel Implant to the desired location.

9.1.2 Instructions for Use and Administration

An investigational directions for use (IDFU) brochure will be provided for the XEN45 Glaucoma Treatment System.

Surgical training will be required and provided by an Allergan representative.

Protocol specific details on administration will be provided in the Protocol Procedure Manual.

9.2 Other Study Supplies

The following supplies will be provided by Allergan or designated suppliers:

- Surgical instruments specific to the surgery for implantation of XEN, including the durable surgical instruments, two sizes of sterile, single use blades and the operative gonio lenses

Sites that are not able to receive supplies from Allergan due to country regulations will need to provide their own supplies.

10. Study Administration Procedures

The clinical study shall not begin until the required approvals from the appropriate regulatory authorities and ECs have been obtained.

10.1 Patient Entry Procedures

10.1.1 Overview of Entry Procedures

Prospective patients, as defined by the criteria in Sections 5.3 and 5.4 (inclusion/exclusion criteria), will be considered for entry into this study. A patient is considered to have enrolled in the study upon signing the informed consent, which occurs prior to any screening procedures. Screening procedures include:

- Collection of demographic information
- Collection of medical/surgical history, including ophthalmic and ophthalmic surgical history.
- Completion of Patient Ocular Symptoms Questionnaire
- Collection of concurrent medications (systemic and ophthalmic) and procedures
- Evaluation of inclusion/exclusion criteria
- Urine pregnancy test (for females of childbearing potential)
- AEs

- Ophthalmic evaluation, which includes the following:
 - IOP
 - Manifest refraction
 - BCVA using LogMar chart
 - Pachymetry
 - Visual field test
 - Biomicroscopic slit lamp examination
 - Gonioscopy
 - Ophthalmoscopy

Note: Photography (or video recordings) are not required by the protocol, but may be taken as part of the investigators' standard practice, and therefore may be collected by Allergan for general research, education, and/or informational purposes. Patients choosing not to allow Allergan permission to use these photography or video recordings taken of them will not be excluded from the study.

10.1.2 Informed Consent and Patient Privacy

The purpose, procedures, risks, benefits, and alternatives to study participation will be discussed with each potential patient. The patient must also give Data Protection Consent and other written documentation in accordance with the relevant country and local privacy requirements (where applicable) prior to any study-related procedures or change in treatment.

The investigator or his/her authorized designee conducts the informed consent discussion and will document in the patient's medical records the acquisition of informed consent and the patient's agreement or refusal to notify his/her primary care physician about the study. The informed consent shall include all aspects of the study that are relevant to the patient's decision to participate throughout the study. The informed consent process is to avoid any coercion or undue influence on, or inducement of, the patient to participate. The patient is to personally sign and date the informed consent. The investigator will retain the original copy of the signed form, and the patient will receive a copy. Upon signing the informed consent form, the patient is considered to be enrolled in the study and receives a patient number that

will be used on all documentation for the patient throughout the study. Patient numbers will be assigned in ascending order, and numbers will not be omitted or reused. The patient number is coupled with the site identification number for unique identification of each patient. The investigator is to ensure important new information is provided to new or existing patients throughout the study.

10.1.3 Method for Assignment to Treatment Groups

All eligible patients will be assigned to treatment with XEN. Investigational product will be labeled with kit numbers that will be recorded on the eCRF.

10.2 Compliance with Protocol

The investigator is responsible for compliance with the protocol at the investigational site. A representative of Allergan will make frequent contact with the investigator and his/her research staff and will conduct regular monitoring visits at the site to review patient and device accountability records for compliance with the protocol. Any protocol deviations will be discussed with the investigator upon identification. All protocol deviations will be reported to the EC according to the EC's reporting requirements.

10.3 Pregnancy

If a female becomes pregnant during the study, the investigator will notify Allergan immediately by completing the Pregnancy Surveillance Form after the pregnancy is confirmed and faxing it to the appropriate number on the front page of this protocol. The investigator shall (1) instruct the patient to notify her physician that they are being treated with an investigational device (ie, XEN) and (2) follow the pregnancy to term. Best practices are to be followed in order to ensure the welfare of the patient and the fetus. Once the pregnancy has reached term, the second page of the Pregnancy Surveillance Form concerning outcome is to be completed. The medical safety physician will contact the investigator to obtain information about the pregnancy outcome. The patient will continue to be followed as part of the implanted population but the pregnancy will be documented as a protocol deviation. Pregnancy by itself will not be considered an AE or serious adverse event (SAE). Hospitalization for a normal delivery or elective abortion of a normal fetus does not constitute an SAE. However, the occurrence of an adverse pregnancy outcome for the mother or child may constitute an AE or SAE, and these are to be reported as described in Sections 11.3 to 11.4.

10.4 Study Termination

If conditions arise during the study that indicate that the study or an investigational site needs to be terminated, the sponsor, investigator, monitor, EC, and/or regulatory agencies will discuss the situation and take appropriate action after consultation. Conditions that may warrant termination of the study or site include, but are not limited to:

- The discovery of an unexpected, serious, or unacceptable risk to patients enrolled in the study
- The decision on the part of Allergan to suspend or discontinue testing, evaluation, or development of the study device
- Failure of the investigator to comply with pertinent national or state regulations, EC-imposed conditions, or protocol requirements
- Investigator submission of knowingly false information to the sponsor, monitor, EC, or any regulatory agency

Per International Organization for Standardization (ISO) 14155, if a study is prematurely terminated or suspended due to safety issues, Allergan shall inform all investigators and the regulatory authorities of the termination or suspension and the reason(s) for the termination or suspension. The EC is also to be informed promptly and provided the reason(s) for the termination or suspension by Allergan or by the investigator, as specified by the applicable regulatory requirements. If a premature termination or suspension occurs, Allergan shall remain responsible for providing resources to fulfill the protocol obligations and existing agreements for follow-up of patients enrolled in the study, and each investigator or authorized designee shall promptly inform enrolled patients, if applicable.

11. Adverse Events

Throughout the course of the study, all AEs will be monitored and reported on an AE eCRF, including seriousness, severity, action taken and relationship to study treatment. If AEs occur, the first concern will be the safety of the study patients.

Although the risk of developing a serious complication is small, the investigator and the research staff will monitor each patient closely, and, if a complication occurs, they will use their medical judgment to do whatever is necessary to treat the problem. Additional information is available in the IDFU.

The following may occur in conjunction with the use of the XEN Gel Implant: Gel Implant migration, Gel Implant exposure or extrusion, Gel Implant blockage, choroidal effusion or hemorrhage, hypotony maculopathy, bleb related complications, or endophthalmitis and other known complications of intraocular surgery (eg, flat or shallow chamber, hyphema, corneal edema, macular edema, retinal detachment, vitreous hemorrhage, uveitis).

Standard of care should be implemented whenever an AE occurs to treat and/or resolve the AE and to monitor the patient. The investigator should ensure the sponsor is kept informed of all details related to the resolution and/or progression of the AE. Any patient who is withdrawn from the study due to an AE shall be followed until the outcome is resolved or, in case of permanent impairment, until the event stabilizes and the overall clinical outcome has been ascertained.

11.1 Definitions

11.1.1 Adverse Event

An AE is defined in accordance with ISO 14155 as “any untoward medical occurrence, unintended disease or injury, or untoward clinical signs (including abnormal laboratory findings) in patients, users, or other persons, whether or not related to the investigational medical device.” This definition includes events related to the investigational medical device or comparator and events related to the procedures involved except for events in users or other persons, which only include events related to investigational medical devices.

Disease signs and symptoms that existed prior to the study treatment are not considered AEs unless the condition recurs after the patient has recovered from the pre-existing condition or the condition worsens in intensity or frequency during the study.

AEs will be monitored throughout the study beginning with signing of informed consent. At each post-baseline visit, the investigator will begin querying for AEs by asking each patient a general, non-directed question such as “Have you had any changes to your condition since your last visit?” Previous AEs and changes in therapy/concomitant medications are to be updated. Directed questioning and examination will then be done as appropriate. All reportable AEs and clinically significant abnormal laboratory findings will be documented on the appropriate eCRF.

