6.1.1 Screening Visit

The window for this visit is up to 60 days prior to surgery. After obtaining informed consent ([Section 10.1.2](#)), the following information will be obtained at this visit:

- Evaluation of inclusion/exclusion criteria
- Patient demographics
- Medical history, surgical history, ophthalmic history, and ophthalmic surgical history, including presence of ocular pathology and concomitant ocular medications (both eyes)
- Patient ocular symptom questionnaire

- Concomitant medications (systemic and ophthalmic) and procedures
- AEs
- Urine pregnancy test (for females of childbearing potential)
- Manifest refraction (both eyes)
- BCVA using LogMar chart (both eyes)
- Visual field testing (both eyes): Monocular visual field testing will be measured using the Humphrey 24-2 full threshold program or Swedish Interactive Thresholding Algorithm (SITA) Standard and a reliable, interpretable visual field will be obtained for patients with a preoperative BCVA of better than 20/100. This assessment is not required for patients with BCVA of 20/100 or worse. Visual field results must be reliable and interpretable, or if unreliable or uninterpretable, the visual field test must be repeated. An unreliable visual field is defined as visual field measurements with > 33% fixation losses, false positives, or false negatives. Visual field test performed up to 6 months prior to operative day (Day 1) is allowed.
- Biomicroscopic slit lamp examination (both eyes): includes determination of ophthalmic medical observations/complications, evaluation of the condition of the eyelids, conjunctiva, cornea, anterior chamber, iris/pupil, and lens (through a dilated pupil).
- IOP (Hour 0 = 8:00 am \pm 1 hour) measurement using Goldmann applanation tonometry (both eyes) using the 2-person reading method (See Protocol Procedure Manual); IOP must be completed prior to pachymetry, gonioscopy, and ophthalmoscopy.
- Pachymetry measurement of central corneal thickness (both eyes) using an ultrasonic pachymeter
- Gonioscopy (both eyes): includes assessment of angle abnormalities, such as peripheral anterior synechiae, angle assessment of each quadrant by Shaffer Grade

- Ophthalmoscopy (both eyes): includes dilated fundus evaluation and vertical cup-to-disc ratio. Non-dilated ophthalmoscopy may be performed if the investigator believes that pupil dilation may put the patient at risk.

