6.1.3 Operative Visit (Day 1)

Patients must be scheduled for surgery within 60 days of screening. The following procedures must be performed prior to the implantation of study treatment:

- Evaluation of inclusion/exclusion criteria
- Medical history, surgical history, ophthalmic history, and ophthalmic surgical history, including presence of ocular pathology and concomitant ocular medications (both eyes)
- Concomitant medications (systemic and ophthalmic [both eyes]) and procedures
- AEs
- Urine pregnancy test (for females of childbearing potential)

The implantation procedure must be performed in an approved surgical suite or operating room using standard aseptic technique and standard ophthalmic surgical techniques to prepare the patient and the operative study eye. Preoperative and intraoperative surgical medications will be administered as customary for the investigator.

[figure not shown]
It is recommended that the target quadrant be the superior nasal quadrant, unless conjunctival scarring will inhibit bleb formation. If implantation is not possible in this quadrant, the order of preference for Gel Implant location is superior temporal, inferior nasal, and lastly inferior temporal.

A detailed description of the XEN surgical procedure is provided in the Protocol Procedure Manual. The general steps of the surgical procedure are as follows:

1. Standard ophthalmic surgery techniques must be used to prepare the patient and the eye. The target area must be pretreated with mitomycin C (see Protocol Procedure Manual for dosing and intraoperative application details).
2. Surgeons may use their standard of care to obtain access to the surgical quadrant. The needle of the sterile XEN Injector preloaded with the XEN Gel Implant is advanced through the peripheral cornea and across the anterior chamber (ie, *ab interno*) toward the targeted quadrant. Corneal entry will be at least 1 to 2 mm anterior to the limbus (ie, not at the limbus or behind it) to ensure proper angulation on the Gel Implant up and away from the iris. The Gel Implant will be placed through the center of the angle.
3. Once the needle is aligned with the desired entry point in the anterior chamber angle, the surgeon advances the needle in the anterior chamber angle and sclera until the surgeon is able to visualize the needle bevel as it exits the sclera into the subconjunctival space.

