### **11.1            ADVERSE EVENTS**

Adverse events will be coded by system organ class and preferred term using the Medical Dictionary for Regulatory Activities, version 21.0 or newer.

An AE will be considered treatment-emergent adverse event (TEAE) if it started after the initiation of XEN implant related procedures.

An overall summary of subject incidences of TEAEs will be presented and will include experiencing the following:

- TEAE (ocular, non-ocular)
- Treatment emergent serious adverse event (TESAE) (ocular, non-ocular)
- TEAE with outcome of death (ocular, non-ocular)
- Study treatment (XEN) related TEAE (procedure related, device related)
- TEAE leading to study treatment discontinuation (XEN device removal)
- TEAE leading to study discontinuation

In general, the number and percent of patients in the Implanted Population reporting TEAEs will be tabulated by system organ class (SOC) in alphabetical order and by preferred term (PT) in descending order of incidence within the SOC, and further categorized by severity and causal relationship to the implant procedure or the device. If

more than 1 AE is coded to the same PT for the same patient, the patient will be counted only once for that PT using the greatest severity and strictest relatedness for the summarization by severity and relationship. These summaries will include:

- Non-ocular TEAEs by SOC, PT and severity grade
- Ocular TEAEs by SOC, PT and severity grade (SE, fellow eye)
- Non-ocular TEAEs by SOC and PT
- Ocular TEAEs by SOC and PT (SE, fellow eye)
- XEN procedure related TEAEs by SOC and PT
- XEN device related TEAEs by SOC and PT
- Incidence of common ( $\geq 5\%$  of patients) TEAEs by PT
- XEN procedure or device related adverse events occurring in  $\geq 2\%$  of the patients by PT
- Serious non-ocular TEAEs by SOC and PT
- Serious ocular TEAEs by SOC and PT (SE, fellow eye)
- TEAEs leading to XEN device removal by SOC and PT
- TEAEs leading to XEN device replacement by SOC and PT
- TEAEs leading to the study discontinuation by SOC and PT

Subject data listings will also be provided to support each summary table.

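### The SAP's onset-only definition of a treatment-emergent AE leaves it to site recording practice whether an AE that begins before implantation and worsens after it is counted

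*Protocol*

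**What the plan says.** **Protocol 11.1.1 (Adverse Event)** opens AE collection at consent: "AEs will be monitored throughout the study beginning with signing of informed consent". Screening may precede surgery by some weeks (6.1.1: "The window for this visit is up to 60 days prior to surgery"). For conditions already present it states: "Disease signs and symptoms that existed prior to the study treatment are not considered AEs unless the condition recurs after the patient has recovered", or unless "the condition worsens in intensity or frequency during the study". On AEs already recorded, the instruction for post-baseline visits is: "Previous AEs and changes in therapy/concomitant medications are to be updated".

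**SAP 11.1 (Adverse Events)** defines treatment emergence in one sentence: "An AE will be considered treatment-emergent adverse event (TEAE) if it started after the initiation of XEN implant related procedures". It then lists summaries by severity, relatedness, seriousness, device removal and study discontinuation. Nearly all are worded as summaries of TEAEs, with listings to support each table.

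Three other places bear on this. Protocol 8.3.4 plans to tabulate AEs without restricting them to TEAEs. SAP 17.0 declares one change from the protocol, and it is not this one. SAP 16.3 imputes a severity for AEs that began before implantation, for use in incidence summaries.

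**The concern.** The protocol recognises two ways in which an earlier condition becomes a reportable harm after implantation: it recurs or it worsens. The SAP recognises only a new start date. If a site follows an AE on one record and updates that record as it progresses, the start date stays before Day 1 and the record fails the SAP test, however severe the event later becomes.

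The period in which such AEs can arise is not trivial. It runs for up to 60 days before surgery and includes the topical corticosteroid course that Protocol Table 6-1 schedules for 5 to 7 days beforehand. Safety is a stated objective alongside effectiveness, in a single-arm study of about 65 patients that the SAP calls pivotal. The TEAE tables carry most of the AE evidence. With up to about 15 sites, the same clinical course could be counted at one site and left out at another.

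**Working it through.** The plan gives no figure on this point to reproduce. The check applies the definitions to an example and then sizes one missed patient.

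**Inputs**
- AE collection starts at consent; earlier AEs are updated; worsening is a ground for calling a prior condition an AE (Protocol 11.1.1).
- Surgery is within 60 days of screening (Protocol 6.1.3).
- The TEAE rule uses onset only (SAP 11.1).
- Day 1 is the implant date, and earlier days are negative (SAP 16.1).
- About 65 patients are implanted (Protocol 5.1; SAP 4.1.2).
- Two summaries in SAP 11.1 have thresholds: 2% of patients for related events and 5% for common events.

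**Step 1: classify one example.** Suppose an AE begins on Day -4 as mild and becomes severe on Day 10.

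| How the site records it | Start date(s) on file | TEAE under SAP 11.1 | TEAE if worsening also counts |
|---|---|---|---|
| One record, updated | Day -4 | No | Yes, if the date of change is held |
| New record at worsening | Day -4 and Day 10 | Yes (Day 10 record) | Yes |

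The clinical course is the same in both rows, but the classification differs. The SAP rule that keeps the greatest severity within a preferred term does not help in the first row, because that record never enters a TEAE table.

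**Step 2: size of one missed patient.** Incidence is k/65, with exact (Clopper-Pearson) 95% limits.
- k = 0: 0%. The upper limit is 1 − 0.025^(1/65) = 5.52%.
- k = 1: 1/65 = 1.54%. The lower limit is 1 − 0.975^(1/65) = 0.04%. The upper limit is the p at which P(X ≤ 1) = 0.025, which is 8.28%.
- k = 3: 3/65 = 4.62%, limits 0.96% to 12.90%.

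**Step 3: effect on the threshold tables.** 0.02 × 65 = 1.3, so two patients (3.08%) are needed for the 2% table and one (1.54%) is not enough. 0.05 × 65 = 3.25, so four patients (6.15%) are needed for the 5% table and three (4.62%) are not enough. At either boundary, one missed patient removes the preferred term from the table.

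The documents do not say how many patients would follow this course, so a total effect cannot be computed. One to three patients is an assumption used to show scale. It corresponds to 1.5 to 4.6 percentage points if all of them fall under one term.

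**The case against.** A reader might infer something stronger: that such an AE is absent from every TEAE table, that the post-operative worsening is lost to the safety analysis, and that the error always favours the device. The documents do not support this, for five reasons.

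1. **The start date is not fixed.** Updating a previous AE could mean only its outcome, stop date or action taken. The completion instructions are not among the documents.
2. **Protocol 11.1.1 can be read the other way.** It covers anything present before study treatment, which includes the interval from consent to Day 1, and makes the worsening the thing that qualifies as an AE. Dated at the worsening, that AE passes the SAP 11.1 test and the two documents agree.
3. **Not every planned summary is limited to TEAEs.** One bullet in SAP 11.1 (related events in at least 2% of patients) is worded as adverse events. Protocol 8.3.4 and SAP 16.3 are not limited to TEAEs either. SAP 4.0 places table and listing specifications in a separate document, so absence from every listing cannot be shown.
4. **Much of the harm is visible elsewhere.** Explants appear in disposition (SAP 7.0) and in the Kaplan-Meier summary (SAP 9.0). Slit-lamp findings at worst severity and acuity line changes are summarised by visit (SAP 11.3), and IOP is modelled from Month 1 (SAP 10.2). SAEs go to the sponsor within 24 hours (Protocol 11.2).
5. **The direction is not strictly one-way.** SAP 16.5 replaces a missing start day with the implant day number, which could move an AE from earlier in the implant month onto Day 1 and perhaps into the TEAE set.

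The exposed group is also narrow: the patient must develop an AE before surgery, still pass the eligibility checks, worsen afterwards and have the worsening entered on the old record.

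All of this limits the consequence. It does not close the gap, because whether the event is counted still depends on an unstated recording convention. The other summaries do not restore AE incidence, severity or relatedness.

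**Conclusion.** The point holds as a gap in definition. SAP 11.1 has no provision for worsening, Protocol 11.1.1 does, and neither says how a worsening is dated. An AE with onset between consent and Day 1 that worsens after implantation can be missing from the TEAE incidence, severity, seriousness and device-removal tables. It will be missing if the site keeps one updated record and the SAP rule is applied as written.

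The size is 1.5 percentage points per missed patient, on the assumption of 65 implanted. The number of such patients is unknown. Apart from the date-imputation accident, leaving out a worsening makes the TEAE tables look more favourable, but how often this would happen cannot be judged from the documents. It is a modest weakness that is cheap to remove, and not evidence that the safety analysis as a whole misses these harms.

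**What to change.** 1. **SAP 11.1.** Extend the definition along these lines: *an AE is treatment-emergent if it started, or if it worsened in severity or became serious, after XEN implant procedures began.*
2. **AE completion instructions.** State that a post-implant worsening of an ongoing AE is entered as a new record dated at the worsening, or that the date of the severity change is recorded on the existing one. Without one of these the extended rule cannot be programmed. The new-record option also handles worsening in frequency, which Protocol 11.1.1 includes but a severity grade would not show.

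The count is then the same under either recording practice. The cost is one SAP sentence and a completion note. AE counts may become slightly less favourable.
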